per cell expression of over 50 differentially expressed molecules. These results will be used to delineate candidate predictor subsets that will be then used as variables to determine the presence of an association with myocardial uptake of FDG. Panels developed in [name] laboratory will be used and will specifically focus on identifying the T reg subset, activated markers on T cells, exhaustion markers, and NK cells. This should result in a much more comprehensive immunologic characterization of the peripheral mononuclear cell alterations in RA and better enable identification of subsets related to myocardial inflammation. Distinctive populations not present in a reference set of RA cases with low or no myocardial FDG uptake will be identified by dimensional reduction analyses and corroborated by gating and biaxial plot analysis. The first step will be flow cytometry and will involve five panels, with each having a Zombie dye for live dead discrimination, CD3, CD4, CD8, CD45RA and CCR7 for identifying subsets across most panels, and on the T cell panels various combination of CD40L, CD31, HLA-DR, CD38, CD69, TIGIT, KLRG1, CD57, CD160, NKG2D, CD28, CD27, CD45RO, PD-1, CD95, CCR2, CCR4, CXCR3, CD39, CXCR5, CD62L, CCR6, CD25, CD161, IFN-γ, IL-17, TNF-α, FOX3P, RORyt, TBX21, GATA3, BCL6, HELIOS, IL-2. The NK/T activation panel also contains CD56, CD16, CD161, CD117, NKp44, NKG2A, CD158a, NKG2D, and CD94. Staining for each panel will be done in 30ul volumes on  $\sim$ 2 x106 MNLs. The cytometry will be done on a 6 laser LSRII. Samples will be run in batches, including samples from different clinical groups within each batch, with care taken to minimize inter-batch variation in staining. Every batch will include a cryopreserved reference normal MNL pool obtained by leukopheresis from 9 normal blood donors by the NY Blood Center, each validated for having a generally normal distribution of subsets and cryopreserved. This reference population will serve as a critical control for machine and technical variations in reagent performance, and will enable the identification of anomalous samples with low viability, enhanced aggregation, or other features suggesting sample processing or transport artifacts. Compensation will be done before each batch. In addition to the classic gating performed in FCS Express software, we will use multiple, complementary dimensional reduction approaches to analyze the multiparametric flow cytometry data (viSNE) as a way to obtain unbiased measures of the cell population alterations. First we will use the t-Distributed Stochastic Neighbor Embedding (t-SNE) algorithm viSNE (64) to visualize the multidimensional data and the various MNL subpopulations among circulating leukocytes (65). Here, the positions of cells on a 2D viSNE plot reflect their proximity in high-dimensional parameter space, including information from each of the dimensions. This unbiased alternative to traditional gating and biaxial subset representation preserves the geometry and nonlinearity of the data, delineates both abundant and rare populations without setting a priori expression criteria, and provides an interpretable data view

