
using color as a third dimensional to show the expression of particular differentiation and activation molecules. A generally similar implementation of viSNE is available in Cytobank, and both algorithms will be used in the delineation of distinctive MNL populations. In viSNE, the gene expression patterns of reference MNLs map into shapes that discriminate between immune subtypes, and the shape of these per cell patterns is altered in disease due to differences in gene expression resulting in patterns that are distinct from the referent control map. The area of the shape is proportional to the size of the population, and viSNE can identify populations consisting of 0.2% of the cell input (64). To compare the T cell subsets, we will first develop a referent viSNE map by overlying similarly grouped subpopulations and cells from the RA patients without myocardial FDG uptake. The similarity of each case subpopulation forming the referent distribution will be determined using the Shannon Diversity Index (SDI)(66), to quantify the similarity between the samples used to make the referent viSNE map. Samples used to make the referent map will be included if their SDI divergence between each pair is <0.05. We will then compare the immune cell populations in those with elevated myocardial FDG uptake by overlying their viSNE transformation to the referent viSNE map of those without FDG myocardial uptake, to define one or more multidimensional phenotypes that differ in each myocarditis patient from the referent. The relation of the population expression patterns to conventional immune subtypes can be corroborated by manual gating of a series of biaxial plots using the molecular markers distinguished in the viSNE plot. The comprehensively defined novel and conventional populations will be designated and their quantitative distribution across the subjects will be tabulated for analysis as predictor variables for Aim 2. As a second alternative and complementary dimensional reduction approach, we will utilize the CITRUS (cluster identification, characterization, and regression) (67) approach implemented through Cytobank (www.premium.cytobank.org). In this method, a modification of SPADE, cells are hierarchically clustered into nodes based on their multidimensional phenotype, and the occupancy of different nodes can be compared quantitatively across individual patients and patient groups. This allows the identification of unique cell populations based on multidimensional phenotypes and then assess for subpopulations that are increased or decreased in groups of patients of interest. Once an altered node is identified, the expression of markers can be assessed to determine defining features of cells in that node. An important feature of CITRUS is that the discovery of statistically significant stratifying MNL subpopulations in these datasets is facilitated by its structure that compares sets of cases across multiple discriminating characteristics (i.e., FDG myocardial uptake positive versus FDG uptake negative). The features of the population(s) defined in viSNE will then be compared with those identified in CITRUS to provide a common set of weighted features. Differences in the putative

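### If the SDI rule removes any FDG-negative samples, the viSNE referent is narrower than the FDG-negative group, and FDG-positive patients are compared with it without a matching rule

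*Combined protocol and SAP*

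**What the plan says.** All of this is in section 5.6 of the combined protocol and SAP (Immunophenotyping of peripheral T cell subpopulations).

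- **Source of the referent:** "we will first develop a referent viSNE map by overlying similarly grouped subpopulations and cells from the RA patients without myocardial FDG uptake".
- **Rule for entering it:** the Shannon Diversity Index (SDI) is used "to quantify the similarity between the samples used to make the referent viSNE map", and "Samples used to make the referent map will be included if their SDI divergence between each pair is <0.05".
- **Comparison:** "We will then compare the immune cell populations in those with elevated myocardial FDG uptake by overlying their viSNE transformation to the referent viSNE map". The aim is "to define one or more multidimensional phenotypes that differ in each myocarditis patient from the referent". No SDI condition is stated for these patients.
- **Use of the result:** the populations are designated and "their quantitative distribution across the subjects will be tabulated for analysis as predictor variables for Aim 2". Candidate expanded populations also go to low-input RNAseq.
- **Second method:** CITRUS "compares sets of cases across multiple discriminating characteristics (i.e., FDG myocardial uptake positive versus FDG uptake negative"), with no SDI condition stated.
- **Technical control:** a pool of normal-donor cells runs in every batch and "will enable the identification of anomalous samples with low viability, enhanced aggregation, or other features suggesting sample processing or transport artifacts".

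The section does not say what happens to FDG-negative samples that fail the rule, how the retained set is chosen when samples conflict, or whether any FDG-negative sample is compared with the map in the way the FDG-positive ones are.

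**The concern.** The rule acts on one side only. Removing FDG-negative samples that do not resemble the others narrows the referent, while the FDG-positive patients keep their full spread. Earlier in section 5.6 the stated target is populations that are absent from a reference set with little or no uptake. A population can be absent from that set simply because the patients who carry it were taken out.

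This differs from selecting and testing subsets in the same patients. It would arise even if discovery and testing used separate patients. At stake is which populations are put forward as possible mechanisms of myocardial inflammation and sequenced.

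**Working it through.** The plan gives no error rate or sample size for this step, so there is no figure of its own to reproduce. The check asks what the rule does when the two groups are identical.

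**Inputs**
- 20 patients (section 6).
- 39% with qualitative uptake in the RHYTHM cohort (section 2.1). If the same share holds here, 0.39 × 20 = 7.8, so about 8 FDG-positive and 12 FDG-negative.
- Threshold 0.05 (section 5.6).
- Assumed, because the documents do not say: one normally distributed SDI value per patient; divergence taken as the absolute difference; the retained set is the largest one with every pairwise difference below 0.05; SD varied from 0.01 to 0.05.

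**Without the rule.** A further value from the same distribution falls outside the range of k referent values with probability 2/(k + 1). For k = 12 this is 2/13 = 15.4%.

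**With the rule** (4,000 simulated studies per SD):

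| SD of SDI | FDG-negatives kept | FDG-positives outside referent range, with rule | Same, without rule |
|---|---|---|---|
| 0.01 | 100% | about 15% | 15–16% |
| 0.02 | 87% | 32% | 15–16% |
| 0.03 | 72% | 51% | 15–16% |
| 0.05 | 54% | 71% | 15–16% |

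**Is this only a smaller referent?** No. A referent of the same size drawn at random from the FDG-negatives gives 15% to 26% over the same SDs. The rest comes from which samples are removed: the extremes.

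**What projecting the FDG-negatives would show.** Under this model every removed sample lies outside the retained range. With the retained set held fixed, its lowest and highest members also fall outside when each is left out in turn. The FDG-negative share outside is then (12 − k + 2)/12, with k = 12 × share kept:
- SD 0.02: k = 10.4, (1.6 + 2)/12 = 30%, against 32% of FDG-positives.
- SD 0.03: k = 8.6, (3.4 + 2)/12 = 45%, against 51%.
- SD 0.05: k = 6.5, (5.5 + 2)/12 = 63%, against 71%.

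Most of the apparent excess disappears once the FDG-negatives are treated alike. The remainder arises because the retained set was chosen with the left-out sample in it. Rebuilding the referent without that sample puts both groups on nearly the same footing.

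**A second model.** All 20 patients were drawn from one Dirichlet distribution over 10 subsets (1,000 runs per setting). Each FDG-positive patient was compared with a 95% prediction interval from the referent, subset by subset. Runs that kept fewer than three FDG-negatives are not in the rates.
- Divergence read as Jensen-Shannon, concentration 400: all 12 FDG-negatives kept, no effect (5.0% outside per subset either way).
- Concentration 100: 11.6 kept on average, 5.5% against 5.2% without the rule.
- Concentration 50: 7.5 kept, 8.7% against 5.2%; 60% against 41% of FDG-positive patients have at least one subset outside.
- Concentration 25: 3.6 kept, 12.4% against 5.5%; 75% against 43%.
- Divergence read as the absolute SDI difference (3.8 to 8.5 kept): 5.9–7.0% against 5.0–5.5% per subset.

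The direction is the same whenever samples are removed. The size depends on the spread and on how divergence is defined.

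**The case against.** Four arguments on the other side have weight.

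1. **The rule may remove nobody.** If all FDG-negative samples lie within 0.05 of one another, there is no added bias. This stands, so the point has to be conditional.
2. **Other steps dilute the effect.** CITRUS states no SDI rule, so removed FDG-negatives can re-enter there, and viSNE and CITRUS features are then compared. Aim 2 tabulates populations across the subjects, and a pattern equally common in the removed patients would tend to show no association with uptake. This stands in part. CITRUS uses the same patients, no text requires a population found only by viSNE to be dropped, and the documents do not settle whether removed patients enter the Aim 2 models. The normal-donor pool does not help here: it detects processing faults and does not equalise biological spread.
3. **The illustration is not the plan's decision rule.** FDG-positive patients are compared by overlay, and no numerical criterion for a difference is given. This also stands. The figures show direction and plausible scale, not an error rate for this trial.
4. **The consequence is limited.** This is discovery work for the secondary objective of a pilot, and section 5.8 concedes that subset detection is limited.

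A reader might go further and count the FDG-positive samples that lie 0.05 or more from some referent member (0.3%, 21%, 41% and 62% at the four SDs), taking that as the harm done by the rule. It is not. With no rule the same count is 0.4%, 44%, 87% and 99.7%. It mainly reflects the assumed SD relative to 0.05, and the rule lowers it. The plan also never scores FDG-positive patients against 0.05.

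**Conclusion.** The asymmetry is in the text, and its consequence is conditional. If the SDI rule removes FDG-negative samples, the viSNE comparison is tilted towards finding differences in FDG-positive patients. If it removes none, it adds nothing. In the one-value illustration the excess over the unfiltered referent is negligible at SD 0.01, about 16 points at SD 0.02 (32% against 15–16%), 35 at SD 0.03 and 55 at SD 0.05. Those figures rest on the 12/8 split, normality, one SDI value per patient and the largest-set reading of the rule. The documents give no spread from which to choose among them, and under the absolute-difference reading the ten-subset model shows only modest inflation per subset.

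The effect is confined to viSNE discovery and the choice of populations for RNAseq. A reader might infer that the Aim 2 associations or the primary result are invalid. The documents do not support that: Aim 2 may use all subjects, and the primary SUV comparison does not use the map. This is a minor point, worth acting on because the remedy is cheap.

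**What to change.** - Keep the SDI rule for drawing the map. State how divergence is computed and how the retained set is chosen when samples conflict.
- Project every technically valid FDG-negative sample onto the map, including those the rule removed, in the same way as the FDG-positive samples. Compare each retained FDG-negative sample with a leave-one-out referent, rebuilt by the same rule without it.
- Carry a viSNE phenotype forward to Aim 2 or RNAseq only if it is more frequent in FDG-positive than in all FDG-negative samples.
- Report how many samples the rule removed.
- Permuting FDG status is optional. If it is done, limit it to the automated steps, because manual gating and back gating cannot be repeated cheaply for each permutation.

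The cost is a little more analysis of data already collected, with no new patients, samples or visits. Fewer candidate subsets may survive.

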
same population between the two methods can be resolved by back gating and analysis of the differences by conventional biaxial displays to characterize the phenotypic elements responsible for divergent classification. Thus, our overall approach in subset definition and discovery combines the respective strengths of CITRUS and viSNE using two different dimensional reduction methods with different down-sampling approaches to confirm the identification of the identified populations, that is ultimately represented in terms of classic biaxial plots. Finally, to further evaluate the potential pathologic functions of candidate expanded T cell populations, the transcriptional phenotype of the cells will be comprehensively delineated by low cell input RNAseq. This will help define the specific immunobiologic characteristics of these particular cellular subsets that are mechanistic candidates to mediate myocardial inflammation. Detailed transcriptomic analyses of selected immune subpopulations will be generated using a method established to characterize PD-1++CD4+ T cells in the circulation of patients with active, seropositive RA (65).

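### Aim 2 picks T cell populations by FDG status and then tests them against FDG uptake at 0.05; where selection and test share scans, the p-values are too small

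*Combined protocol and SAP*

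**What the plan says.** Section 3.2 makes the association between T cell subsets and myocardial FDG uptake the secondary objective and says that it will be tested. Section 5.6 sets out how the subsets are found. The cytometry results will "delineate candidate predictor subsets that will be then used as variables to determine the presence of an association with myocardial uptake of FDG". The search is defined by FDG status: "Distinctive populations not present in a reference set of RA cases with low or no myocardial FDG uptake will be identified". In viSNE, a referent map is built from patients without uptake, and the team will then "compare the immune cell populations in those with elevated myocardial FDG uptake by overlying their viSNE transformation to the referent viSNE map".

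The outcome of that step feeds the models. Of the populations so found and the conventional ones alike, the plan says that "their quantitative distribution across the subjects will be tabulated for analysis as predictor variables for Aim 2". CITRUS follows as a second method, again contrasting FDG-positive with FDG-negative patients. The viSNE features "will then be compared with those identified in CITRUS to provide a common set of weighted features". The section presents the combination as "using two different dimensional reduction methods with different down-sampling approaches to confirm the identification of the identified populations".

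Section 12.1 relates T cell subpopulations to FDG uptake by linear mixed models within each treatment arm and sets two-tailed 0.05 as the significance level for all tests. Section 5.1 has the subpopulations evaluated at both visits. Section 5.8 warns that associated subsets may be missed in a small sample; it says nothing about false positives.

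**The concern.** The same information is used twice. A population is chosen because it differs between patients with and without FDG uptake, and is then tested for association with FDG uptake, apparently in the same patients. Chance differences that got a population chosen also help it pass the test. A p-value from section 12.1 does not allow for this.

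Conventional subsets that are not chosen by FDG status do not share that problem, but they face a second one: many subsets, two arms, and 0.05 each time.

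At stake is what Aim 2 may conclude. Under the plan as written, an FDG-selected population with p<0.05 would be called significant although part of that result comes from selection. Section 5.6 then sends candidate expanded populations to RNAseq as possible mediators of myocardial inflammation.

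**Working it through.** **1. Does selection share information with the test?** Section 2.1 ties status to SUV: median SUV mean 2.8 in patients with visible uptake against 1.6 without, p<0.0001. Section 5.6 tabulates the selected populations across the subjects, section 5.1 evaluates both visits, and section 12.1 uses a mixed model, which would naturally take both. Shared patients and scans are therefore the natural reading. It is not stated outright: the visit that defines FDG status and the cut-off for elevated uptake are not given.

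**2. The plan's own figure.** There is none for Aim 2 beyond the nominal 0.05. The power statement in section 12.2 concerns Aim 1.

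**3. Inputs for an illustration.**
- From the documents: 10 patients per arm; FDG-positive share 39%, so 0.39 × 20 = 7.8, taken as 8 of 20.
- SUV spread, from the section 2.1 quartiles as ln(Q3/Q1)/1.349: all patients ln(2.6/1.5)/1.349 = 0.408; positive ln(4.9/2.2)/1.349 = 0.594; negative ln(1.9/1.4)/1.349 = 0.226.
- Assumed: within-patient correlation 0.3-0.7 between visits and the selection rules below. T cell values are generated unrelated to SUV, so every significant result is false.

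**4. Null simulation, test within an arm of 10 at two-sided 0.05.** The two-visit runs used a random-intercept model of log SUV on the T cell value with a visit effect. The one-visit runs used a simple correlation.

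| How the population was chosen | Null tests significant |
|---|---|
| Without FDG status | 5-6% |
| Near to viSNE: at least 2 or 3 of the 8 positive patients above every negative one | about 6-10% |
| t-test-like screen of positive against negative | about 8-19% |
| Either rule, selected at one visit and tested only at the other | about 4-7% |

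Within the third row, the two-visit model gives 8-15% with a baseline screen and 15-17% if status is taken scan by scan; the one-visit version gives 11-19%.

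**5. Conventional subsets.** For m independent subsets tested in two arms, P(at least one false positive) = 1 - 0.95^(2m). The counts of 10 and 20 are assumed. Subsets gated on shared markers overlap, so correlated values are shown too.

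| Correlation between subsets | m = 10 | m = 20 |
|---|---|---|
| 0 | 1 - 0.95^20 = 64% | 1 - 0.95^40 = 87% |
| 0.5 | about 53% | about 71% |
| 0.7 | about 41% | about 55% |

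**The case against.** The best defence is context. Section 12 calls this a pilot and a proof of concept, section 5.6 speaks of candidates, section 5.8 asks for a larger blinded trial if the preliminary data are confirmed, and no decision rule hangs on an Aim 2 p-value. This limits the consequence. It does not remove the problem: no test is exempted from 0.05, section 3.2 promises a test, and section 5.8 discloses only missed associations.

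The second defence is that the bias is not inevitable, and that stands. If populations were selected at one visit and tested only at the other, the error rate would be close to nominal. The text also does not say outright that the reference RA cases are trial patients; an external discovery set would remove the selection bias, though not the multiplicity. But no such set is named. The only outside samples described are pooled normal donor cells used as a technical control.

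The third is that no t-test screen appears in the plan. That also stands, so the rule nearer to viSNE is the better guide. A reader might take from the stronger screen that 16-47% of null trials would yield a false association with 20-50 independent candidates. That rests on an assumed screen and an assumed count, and the documents support neither.

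Finally, that CITRUS populations enter the models is inferred from the common feature set, and any error control inside the cited CITRUS method cannot be seen from these documents. The viSNE route is explicit and carries the point without it.

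**Conclusion.** The point holds, conditionally. Where selection and test share trial patients and scans, which is the natural reading, p-values for FDG-selected populations are too small. The size is illustrative, because the selection rule, the number of candidates and the visit are not given: about 6-10% under a rule near to viSNE, and up to 19% under a stronger screen, against 5-6% unselected.

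Three stronger inferences are not supported. The inflation is not certain, since separate visits or an external discovery set would largely or wholly remove it. Conventional subsets fixed without FDG status are not selection-biased; they carry only multiplicity, and 64% or 87% is the independent-subset figure, not the expected one. The per-arm model and the primary comparison of FDG change between arms are not affected.

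Agreement between viSNE and CITRUS does not rescue the p-values: both use FDG status, and no separate cohort is described. Severity is minor to moderate, for a secondary objective of a pilot.

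**What to change.** **Main change, two sentences, same samples and assays.**
- In section 12.1: populations chosen with any use of FDG status, by the viSNE referent contrast or by CITRUS, are hypothesis-generating. They are reported with estimates and intervals and a note that selection makes these optimistic, without a significance claim at 0.05.
- In section 5.6: agreement between viSNE and CITRUS is consistency on the same samples, not independent confirmation.

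**Optional, only if some Aim 2 association is to keep a significance claim.**
- Fix a short list of subsets without FDG status and apply false discovery control over all of them and both arms. The cost is power. At 10%, a lone association must reach p ≤ 0.10/(2m): 0.01, 0.0025 or 0.001 for 5, 20 or 50 subsets. In a one-visit correlation with n = 10, |r| = t/√(8 + t²) gives thresholds of 0.765, 0.837 or 0.872, against 0.632 at 0.05. For a true r of 0.7, power falls from 68% to about 40%, 20% or 12%. Section 12.1 would also have to reconcile the 10% rate with its 0.05 rule.
- Or permute each patient's FDG data (status and both SUVs together) within arm and repeat the selection and test steps. With 20 candidates at correlation 0.5 and the t-test screen, this gave a family-wise rate of 4.7-6.0%, against 15.0-20.5% uncorrected. It needs more programming and covers only automated steps, not manual or back gating.
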